8.4.4 Other safety evaluations

Renal function

Renal function will be assessed at each visit by measuring serum creatinine and utilized to calculate the estimated glomerular filtration rate (eGFR) using the MDRD-4 formula.

New onset diabetes mellitus

New onset diabetes mellitus is defined as:

All of the following should be true (no diabetes mellitus pre-transplantation):

- Diabetes was not included in the medical history.
- Glucose (random) <11.1 mmol/L (200 mg/dL) at the time of transplantation.
- Diabetes was not recorded as reason for any medication given prior to transplantation.
- HbA1c <5.7% at the time of transplantation.

And at least one of the following should be true (diabetes onset after randomization):

- Two consecutive fasting plasma glucose (FPG) ≥126 mg/dL (7.0 mmol/L) at any time after Day 29 or a random plasma glucose (RPG) ≥200 mg/dL (11.1 mmol/L).
- HbA1c \geq 6.5% (only from Day 85 forward).
- Diabetes reported as an AE that is prevalent after Day 29.
- Any concomitant medication with Anatomical Therapeutic Chemical (ATC) level 2 code "A10" (drugs used in diabetes), if prevalent after Day 29.

Definitions for diabetic related diagnoses are according to the American Diabetes Association 2013 and [WHO-ADA criteria].

Hepatic Artery Thrombosis

Hepatic Artery Thrombosis (HAT) are frequent in this population and will be recorded as Adverse Events or Serious Adverse Events as appropriate. The treatments given should be recorded on the Concomitant Medications and/or the Surgical and Medical Procedures CRF (e.g., re-anastomosis, stent, etc.) as appropriate.

Malignancies

For participants on study treatment and in follow-up, any type of malignancy (including skin neoplasms, leukemia, post-transplantation proliferative disorder (PTLD)) should be reported as a SAE and recorded on the appropriate CRFs. A SAE report should be completed for malignancies occurring until the last visit (for participants in follow-up) or for 14 weeks after the last dose of study treatment taken, (for participants in the treatment period or who completed the treatment period).

Hepatocellular carcinoma (HCC) recurrence

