AEs and infections data will be analyzed as a whole under the heading of AEs for each treatment arm. If a participant has multiple occurrences of an AE, the participant will only be counted once in the corresponding AE category. If participant has multiple AEs within a SOC, the participant will be counted only once for that SOC. If a participant has multiple severity ratings for an AE, the participant will be counted under the maximum rating.

New onset of diabetes mellitus (NODM)

The new onset diabetes mellitus is defined in Section 8.4.4

If any of the criteria for diabetes prior transplantation is unknown (e.g., lab values) and all other criteria are true, the subject will be considered to have no diabetes pre-transplant.

The proportion of participants developing new onset diabetes mellitus after transplantation (NODM) will be summarized by treatment arm. The probabilities of developing NODM will be compared between treatment arms at Month 12 and at Month 24 post-transplantation using logistic regression models with treatment arm and HbA1c levels at randomization as explanatory variables. Death, graft loss, or loss to follow up without NODM before Month 12

(or 24) will not be counted as developing NODM. This analysis will be performed using participants in the FAS population who do not have diabetes mellitus at randomization.

Vital signs

Summary statistics will be provided by treatment and visit/time.

12-lead ECG

All ECG data will be listed by treatment arm, participant and visit/time. Summary statistics will be provided by treatment and visit/time.

Clinical laboratory evaluations

Summary statistics (mean, standard deviation, minimum, median, maximum) of quantitative lab variables, including change from randomization, will be provided by parameter, treatment, and visit.

Renal function will be plotted over time.

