16.5 Appendix 5: American Diabetes Association criteria for Diabetes

As defined by the American Diabetes Association:

Diabetes is diagnosed when any of the following are present:

- Symptoms of diabetes, plus casual plasma glucose $\geq 200 \text{ mg/dL}$ (11.1 mmol/L).
- Two consecutive fasting plasma glucose (post-transplantation) \geq 126 mg/dL (7.0 mmol/L)
- 2-hour post-load plasma glucose ≥ 200 mg/dL (11.1 mmol/L) during a 75 gram (g) oral glucose tolerance test.
- HbA1c \geq 6.5% post-transplantation.

Results obtained by each method must be confirmed on a different day unless definite symptoms of hyper glycemia are present.

- Impaired fasting glucose is a fasting plasma glucose 100 mg/dL (5.6 mmol/L) to 125 mg/dL (6.9 mmol/L).
- Impaired glucose tolerance is a 2-hour post-load plasma glucose 140 mg/dL (7.8 mmol/L) to 199 mg/dL (11.0 mmol/L) during a 75 g glucose tolerance test.

Reference: Diagnosis and Classification of Diabetes Mellitus, American Diabetes Association (2013), Diabetes Care 2013; 36 Suppl 1:S11.

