 - 4. HbA1c < 5.7% at the time of transplantation
 - 5. If any of the above criteria is unknown (e.g. lab values), the participant will be considered to have no diabetes pre-transplant if all other criteria are true;

AND

- b. At least one of the following should be true (diabetes onset after transplantation):
 - 1. Two consecutive fasting plasma glucose (FPG) \geq 126 mg/dL (7.0 mmol/L) any day after Day 29 or a random plasma glucose (RPG) \geq 200 mg/dL (11.1 mmol/L).
 - 2. HbA1c \geq 6.5% (only from Day 85 onward).
 - 3. Diabetes reported as an AE that is prevalent after Day 29.
 - 4. Any concomitant medication with ATC level 2 code "A10" (drugs used in diabetes), if prevalent after Day 29. Here "prevalent after Day 29" means the described drug has been consecutively used for at least 30 days since Day 29.

Note that participants with steroid-induced diabetes are excluded. The date of onset is the earliest date when any of the conditions in Criterion b above is met. The proportion of participants developing new onset diabetes mellitus (NODM) after transplantation will be summarized by treatment group. Death, graft loss, or loss to follow up without NODM before Month 12 will not be counted as developing NODM. This analysis will be performed using

participants in the FAS population who do not have diabetes mellitus at the time of transplantation according to Criterion a.

Disclosure reporting

For the legal requirements of ClinicalTrials.gov and EudraCT, two required tables on treatmentemergent adverse events which are not serious adverse events with an incidence greater than 5% and on treatment emergent serious adverse events and SAE suspected to be related to study treatment will be provided by treatment, system organ class and preferred term on the SAF.

If for a participant, several consecutive AEs (irrespective of study treatment causality, seriousness and severity) occurred with the same SOC and PT:

- a single occurrence will be counted if there is ≤ 1 day gap between the end date of the preceding AE and the start date of the consecutive AE
- more than one occurrence will be counted if there is > 1 day gap between the end date of the preceding AE and the start date of the consecutive AE

For occurrence, the presence of at least one SAE / SAE suspected to be related to study treatment / non SAE has to be checked in a block e.g., among AE's in a ≤ 1 day gap block, if at least one SAE is occurring, then one occurrence is calculated for that SAE.

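### The random-glucose criterion for new onset diabetes has no start day, and the SAP's transplantation anchor lets a single value taken before study treatment count as an event

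*SAP*

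**What the plan says.** SAP Section 2.7 (NODM) requires no diabetes before transplantation (criterion a) and at least one onset condition (criterion b). The time limits within criterion b are:

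- **Fasting glucose:** two consecutive values of 126 mg/dL or more, after Day 29.
- **Random glucose:** 200 mg/dL or more, in the same item after the word "or", with no day and no repeat: "any day after Day 29 or a random plasma glucose (RPG".
- **HbA1c of 6.5% or more:** "only from Day 85 onward".
- **Adverse event:** "Diabetes reported as an AE that is prevalent after Day 29".
- **Antidiabetic medication:** "drugs used in diabetes), if prevalent after Day 29", which the SAP explains as at least 30 consecutive days of use since Day 29.

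The SAP heads this list "At least one of the following should be true (diabetes onset after transplantation", takes as onset the earliest date on which any condition is met, and analyses FAS participants free of diabetes at transplantation.

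Protocol Section 8.4.4 has the same undated random-glucose limb, but under a different heading: "And at least one of the following should be true (diabetes onset after randomization". Protocol Section 12.5.2.2 restricts the analysis to "participants in the FAS population who do not have diabetes mellitus at randomization".

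Protocol Appendix 5 accepts a casual glucose of 200 mg/dL or more only together with symptoms, and adds: "Results obtained by each method must be confirmed on a different day unless definite symptoms of hyper glycemia are present".

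**The concern.** The start days keep early post-transplant hyperglycaemia out of the event count. The random-glucose limb escapes that filter, although it needs only one reading. In the protocol the gap is partly closed by the randomisation heading and at-risk set. The SAP removes both limits.

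During the run-in all participants have the same tacrolimus target (5-15 ng/mL, protocol Section 4.1), and corticosteroids are mandatory until the Month 4 visit (protocol Section 3). A high glucose in that week says nothing about the randomised regimens. Counting it as NODM gives an onset date that can precede the first CFZ533 dose and blurs a contrast in which the protocol (Section 4.6) expects less NODM on CFZ533.

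**Working it through.** **Which days qualify under each text.** Days count from transplantation (Day 1), as in the protocol schedule.

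| Random glucose of 200 mg/dL or more taken | Protocol 8.4.4 and 12.5.2.2, literal | SAP 2.7, literal |
|---|---|---|
| After transplantation, before randomisation (Day 8±2) | No: onset must follow randomisation | Yes |
| After randomisation, up to Day 29 | Yes | Yes |
| After Day 29 | Yes | Yes |

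The first row is opened by the SAP alone. The second is a gap in both documents. SAP Section 2.7.3 runs laboratory analyses from liver transplantation, so early values are not plainly removed elsewhere.

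**Direction.** A participant with an early event is counted whichever arm follows, so that person contributes nothing to the arm difference. If a share q of every arm has an early event:

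observed rate = q + (1 − q) × p, so observed difference = (1 − q) × (p_control − p_CFZ533)

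Here p is the later rate among those without an early event. The illustration takes the later effect to be the same in those with an early event. Before randomisation q is common to the arms in expectation.

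**Inputs.** The plan gives no NODM rate, power or sample size, so there is no figure to reproduce. For illustration, p_control = 0.30 and p_CFZ533 = 0.125, from the kidney proof-of-concept trial quoted in protocol Section 4.7. The documents do not give that trial's NODM definition. The early rate q is not in the documents; the values below are assumptions.

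| q | Control | CFZ533 | Difference (points) | Risk ratio |
|---|---|---|---|---|
| 0 | 30.0% | 12.5% | 17.5 | 0.42 |
| 5% | 33.5% | 16.9% | 16.6 | 0.50 |
| 10% | 37.0% | 21.3% | 15.8 | 0.57 |
| 20% | 44.0% | 30.0% | 14.0 | 0.68 |
| 40% | 58.0% | 47.5% | 10.5 | 0.82 |

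For q = 10%: control 0.10 + 0.90 × 0.30 = 0.370; CFZ533 0.10 + 0.90 × 0.125 = 0.2125; difference 0.1575.

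**After randomisation.** From Day 8, tacrolimus is weaned in Arms 2 and 3 (off by Day 22) and continued in Arm 1, so early rates may differ. With rates q_c (control) and q_t (CFZ533):

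difference = 0.175 + 0.70 × q_c − 0.875 × q_t

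This is below 17.5 points only if q_c/q_t < 0.875/0.70 = 1.25. With 15% in control and 10% on CFZ533, the rates are 40.5% and 21.3%. The difference is 19.3 points, wider than without early events, although the risk ratio still moves from 0.42 to 0.53.

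**The case against.** Several things limit the point.

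- **Reading across the "or".** Both glucose conditions are one numbered item, and a programmer could apply Day 29 to both. The Amendment 3 rationale, which sets Day 29 for assessments after randomisation and names no exception for random glucose, fits that intent. The wording does not secure it, and two readings giving different counts still need settling.
- **On-treatment default.** SAP Sections 2.1.2 and 2.7 use on-treatment data for safety unless otherwise specified, and NODM has no explicit data window. If the default applies, values before the start of treatment drop out. But NODM is specified on the FAS with onset after transplantation, so this is unsettled. Values between the start of treatment and Day 29 would count either way.
- **Steroid-induced diabetes is excluded** in the SAP. This may remove early cases, but no rule says how they are identified while all arms take steroids.
- **Few values may exist.** SAP laboratory summaries use central data, protocol Table 8-5 lists glucose as fasting, and Table 8-1 schedules no central safety laboratory test between baseline and randomisation. The source of a random glucose is not stated. This stands, and makes the upper early rates hard to support.
- **Disclosure.** SAP Section 2.1 says analyses may differ from the protocol because of early termination. That general notice does not explain this change, and Section 4 lists none.
- **The protocol's at-risk set is itself undefined.** Neither document says how diabetes at randomisation is determined; the listed pre-existing-diabetes criteria refer to transplantation or earlier. This stands and shapes the fix.

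A reader might infer that early hyperglycaemia is added equally to all arms and hides a CFZ533 benefit. The documents do not support that. Equality follows only before randomisation, the early rate is unknown, and at 10% the illustrated difference is still 15.8 points.

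**Conclusion.** The defect is in the rule as written. The random-glucose limb is the only undated onset criterion, one value meets it, and the SAP's transplantation anchors let that value be dated before study treatment. Dilution follows by design for events before randomisation, provided the later effect among those participants is not reversed. For Day 8 to Day 29 the direction is uncertain.

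The size cannot be determined from the documents. The fall from 17.5 to between 15.8 and 10.5 points is an illustration resting on borrowed kidney-trial rates and assumed common early rates of 10% to 40%. It is not an estimate for this trial.

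The stakes are limited. The SAP only summarises NODM proportions by arm; the protocol's logistic comparison is gone, no test or decision rule uses the result, and the study ended early with an abbreviated report. The definition should still be corrected, because the reported proportion and onset dates depend on it.

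**What to change.** 1. Apply the after-Day-29 start to the random-glucose limb in SAP criterion b.1 and protocol Section 8.4.4. State the day origin, since SAP Table 5-1 counts window days from first treatment.
2. Restore the protocol's heading of onset after randomisation, so that no onset date precedes study treatment.
3. Exclude from the at-risk set anyone who already meets an onset criterion at or before randomisation, with the thresholds read without their start days for this purpose. This gives the protocol's undefined population a working definition.
4. State the data source for random glucose (central, local or unscheduled) and how steroid-induced cases are identified.
5. Reconcile the single-value rule with the symptom and confirmation requirement in Appendix 5.
6. Record any remaining departure from the protocol in SAP Section 4.

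The cost is a few sentences and a date filter in the derivation. The downside is that slightly fewer NODM events are counted, and the denominator may shrink a little.

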2.7.2 Deaths

In addition to the output required for disclosure, the number of deaths will be tabulated by treatment.

2.7.3 Laboratory data

Analyses of laboratory data include data since baseline (liver Tx) but changes are calucated based on the day of randomization. Summary statistics (mean, standard deviation, minimum, median, maximum, and 25% and 75% percentiles) of quantitative lab variables, including change from randomization, will be provided by parameter, treatment, and visit. Similarly, proportion of notable abnormalities of key laboratory tests (Table 5-4) by parameter, treatment, and visit and its listing will be provided. Shift tables using the normal/abnormal classification will be used to compare randomization to the worst on-treatment value.

The following lab parameters will be presented: liver function (AST, ALT, GGT, ALP, and total bilirubin), renal function (eGFR, creatinine, and urine protein/creatinine ratio), lipids, and hematology (WBC, neutrophils, and lymphocytes). eGFR will also be summarized by CKG stages (< 15, [15, 30), [30, 45), [45, 60), [60, 90), and \geq 90) by treatment arm and by visit.

Liver events will be presented as defined in Table 5-6.

Average duration of infection-free period will be presented by treatment. The frequency of following categories will also be summarized by treatment:

- EBV: > 2000 copies/mL;
- CMV: ≤ 5000, (5000, 1000], and > 10000 copies/mL;

For CFZ533 participants, the counts will be provided separately for participants who remain on CFZ533 vs. those who switch from CFZ533 to discontinuation or to SOC. In participants who switch from CFZ533, summary statistics of the mean time from the end of switch to viral load elevation (EBV > 2000 copies/mL, CMV > 10000 copies/mL) will be provided. A listing of participants above the thresholds will be provided by treatment and visit. The day of end of switch is the same as the day of discontinuation of CFZ533 (defined in Section 2.1.1).

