2.1 Data analysis general information

Due to the early termination of the study, the analysis plan has been modified and may be different from the Protocol.

The primary analysis will be performed after all participants have completed the Month 12 visit, or prematurely discontinued study before Month 12. These analyses will be performed by a Contract Research Organization, ICON. Interim analyses, detailed in Section 2.13, will be performed also by ICON.

The following general data conventions will apply:

- Cut-off day is defined as the latest study day before or up to which data will be used in the • analysis. Note that safety data collected during the Safety Follow-up period after EOS is reported to Novartis/Safety and will be included in relevant analyses.
- Descriptive statistics will be calculated based on observed values. Missing values will be • presented separately for each parameter or category. Categorical data will be presented as frequencies and percentages. For continuous data, n (sample size), mean, standard deviation, median, 25th and 75th percentiles, minimum, and maximum will be presented.
- BPAR will be based on centrally blinded adjudicated data. All other efficacy • endpoints will also be based on central

lab data.

- AE, SAE, Infection, Serious Infection (including malignancies), CMV information, and • EBV information will be summarized based on all eligible collected events.
- All lab and vital sign tables will include data since baseline (liver Tx) but changes are calculated based on the day of randomization. All summaries are based on central lab data.

Novartis	
SAP	

- Efficacy and liver function analyses are based on all available data including those after study medication discontinuation or as a supportive analysis based only on on-treatment values. Participants are censored for the time-to-event analyses if they do not have an event. For on-treatment analysis, the censoring day is the date of discontinuation of study treatment (defined in Section 2.1.1); for the all-data analysis (regardless of on-treatment or off-treatment), the censoring day is the last contact day.
- Listings will only be provided for variables explicitly indicated in this SAP. Listings will include all available data.

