2.1.1 General definitions

For the purposes of statistical analysis, "study treatments" are and will be displayed in the outputs as CFZ533 300mg + MMF, CFZ533 600mg + MMF, and TAC + MMF. "Baseline" is defined as the last assessment, including unscheduled assessments, performed prior to liver Tx. All assessments obtained after liver Tx are considered as post-baseline unless otherwise specified. Only centrally adjudicated data will be used for efficacy analyses and laboratory (including vital signs).

In the event that a participant only takes one of the three treatments, the following definitions apply:

- Start of study treatment:
 - a. CFZ533 arms: day of the first loading dose of CFZ533 on Day 8±2 post-LTx.
 - b. Control arm: Day 8 post LTx.
- End of study treatment:
 - a. CFZ533 arms: day of the last dose of CFZ533 +14 days. If a participant in CFZ533 arms discontinues treatment before Day 8±2 (first dose of CFZ533), the rules of control arm apply.
 - b. Control arm: day of the last dose of TAC.

In calculating the duration of treatment, days of permitted interruption of study medication (CFZ, TAC, and MMF) for any reason will be included (see Section 6.5 in the Protocol for details on permitted dose interruption). The entire treatment period is divided into three parts: Treatment Period 1, 2, and 3 (see Section 1.1).

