2.1.2 Analysis sets

The screened set (SCR) consists of all participants who signed the informed consent. The screened set includes only uniquely screened participants, i.e., in the case of re-screened participants, only the chronologically last screened data is counted. Screening phase disposition will be based on the SCR.

The randomized set (RND) consists of all participants who signed the informed consent and were randomized, including misrandomizations.

The full analysis set (FAS) will include all participants who were transplanted and randomized, excluding mis-randomized participants. Mis-randomized participants are defined as cases where IRT contacts were made by the Investigator/qualified site staff either prematurely or inappropriately to confirmation of the participant's final randomization eligibility and treatment was not administered to the participant. Following the intention-to-treat (ITT) principle, participants will be analyzed according to their treatment assignment at randomization. Participant demographics, baseline characteristics, efficacy and renal function measured by GFR will be performed on the FAS.

The safety set (SAF) consists of all participants in FAS who received at least one dose of study drug (i.e., at least one dose of TAC after randomization in the Control arm and at least one dose of CFZ533 in the CFZ533 arms). Participants will be analyzed according to the treatment they actually received. All safety analyses, including renal function parameters other than GFR, will be performed on the SAF using on-treatment (between start and end of treatment defined in Section 2.1.1) data unless otherwise specified.

The PK analysis set (PKS) will include all participants with at least one available valid (i.e., not flagged for exclusion) PK concentration measurement, who received any study drug and with no protocol deviations that impact on PK data, e.g. if a dose was taken more than 7 days after the planned date.

The total screened participants and each analysis population above will be summarized in terms of the frequencies and percentages. Listings of randomized participants and of the participants excluded from analysis sets will be provided.

Rules for exclusion from analysis sets is in Table 5-9.

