2.7 Safety analyses

The SAF will be used for safety analyses unless otherwise specified. General safety summaries (tables, figures, etc.) will include only data from the on-treatment period with the exception of baseline data which will also be summarized where appropriate (e.g., change from baseline summaries), unless otherwise specified. For CFZ533 arms, the on-treatment period lasts from the date of first administration of study treatment to 14 days after the date of the last actual administration. For the Control arm, it lasts to the day of the last actual administration of TAC.

Adverse events (AEs) will be presented and summarized for all treatment-emergent events, with a start date after randomization and covering until 14 weeks after the last administration of CFZ533 for CFZ533 arms and 12 weeks after that of TAC for TAC arm. In addition, a separate summary for death will be provided. Malignancies are summarized under SAEs.

All information obtained on adverse events will be displayed by treatment group. The number and percentage of participants with treatment-emergent adverse events and serious adverse events (events started after the first dose of study medication or events present prior to start of treatment but increased in severity based on preferred term) will be summarized in the following ways:

- by treatment, primary system organ class and/or preferred term
- by treatment, primary system organ class, preferred term and/or maximum severity

Separate summaries will be provided for AEs leading to treatment discontinuation.

In addition, the proportion of participants with infections will be summarized as follows:

- Infections by type of infection (viral, fungal, bacterial, others) and severity.
- Serious infections by type of infection (viral, fungal, bacterial, others) and severity.

The incidence rate of infection by type (viral, bacterial, fungal, and others) will be tabulated for each treatment arm. The key safety parameter is serious infections. The number of serious infections will be used to evaluate the stopping rule as outlined in Section 9.1.5 in Protocol.

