5.5.1 Exposure-adjusted incidence rate and 100(1 - α)% confidence interval

Exposure-adjusted incidence rates is presented per 100 participant-years. Participant-years is calculated as a sum of individual participant durations in days divided by 365.25.

It will be assumed that for each of *n* participants in a clinical trial the time t_j , (j = 1, ..., n) to the first occurrence of a certain treatment emergent event is observed, or if the event was not experienced, the (censored) time to the end of the observation period or EOT, whichever occurs earlier. The sequence of first occurrences of an event will be modeled to follow approximately a Poisson process with constant intensity θ . The rate parameter θ will be estimated as $\lambda = D/T$, where $T = \sum_{j=1}^{n} t_j$ and D is the number of participants with at least one event. Conditionally on T, an exact $100(1 - \alpha)\%$ confidence interval for a Poisson variable with parameter θT and observed value D can be obtained based on (Garwood, 1936), from which an exact $100(1 - \alpha)\%$ confidence interval for $\lambda = D/T$ will be derived as follows (Sahai, 1993; Ulm, 1990):

Lower confidence limit
$$L = \frac{0.5\chi_{\frac{\alpha}{2},2D}}{T}$$
 for $D > 0$, and $= 0$ otherwise;

Upper confidence limit $U = \frac{0.5\chi_{1-\frac{\alpha}{2},2D+2}}{T}$.

where $\chi_{\alpha,k}$ is the α -th quantile of the Chi-square distribution with k degrees of freedom.

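### The average infection-free period in SAP 2.7.3 is undefined, and a plain average would depend on how long each arm was observed as well as on infection risk

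*SAP*

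**What the plan says.** SAP 2.7.3 (Laboratory data) gives this summary one sentence: "Average duration of infection-free period will be presented by treatment". It comes just before the EBV and CMV viral-load categories, so it is unclear whether any infection counts or only viral ones. No start date, end date, estimator or rule for participants without infection is stated.

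Three observation windows appear elsewhere in the SAP:

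- **On-treatment (default).** SAP 2.1.2 runs safety analyses "using on-treatment (between start and end of treatment defined in Section 2.1.1) data unless otherwise specified". SAP 2.1.1 ends treatment differently by arm: "CFZ533 arms: day of the last dose of CFZ533 +14 days" against "Control arm: day of the last dose of TAC".
- **Adverse-event window.** SAP 2.7 counts treatment-emergent events "covering until 14 weeks after the last administration of CFZ533 for CFZ533 arms and 12 weeks after that of TAC for TAC arm".
- **All data.** SAP 2.1 lists infections, serious infections and CMV together, and ends the list: "EBV information will be summarized based on all eligible collected events".

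SAP 5.5.1 has an explicit censoring rule for exposure-adjusted incidence rates: follow-up runs to the first event, "or if the event was not experienced, the (censored) time to the end of the observation period or EOT, whichever occurs earlier". SAP 2.13 uses exposure-adjusted rates for infections at the interim analysis. Neither section is linked to the infection-free period.

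**The concern.** A participant who never has an infection has no infection date. The only duration available is the time observed. A plain mean must therefore either mix infection times with observation times or drop the uninfected participants. Both versions depend on length of observation.

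Under the on-treatment default, observation ends when treatment ends, and time on treatment can plausibly differ by arm:

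- Protocol 6.6.2 takes a CFZ533 participant off randomized treatment if tacrolimus is needed for rejection, whereas a control participant can have tacrolimus increased and continue.
- Protocol 6.5.2 provides for stopping CFZ533 when over-immunosuppression is severe or persists.
- The 14-day tail in SAP 2.1.1 is given to the CFZ533 arms only.

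Infection is a central safety question for an immunosuppressant, and the trial was terminated on risk-benefit grounds (SAP 1). A by-arm infection duration will be read as comparative safety evidence, although it may partly reflect who stayed on treatment.

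**Working it through.** The plan states no figure for this summary, so there is nothing to reproduce. The check asks what a plain average shows when infection risk is identical in both arms.

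**Inputs**
- Month length is 28 days (SAP 5.1), so 12 months is τ = 336 days.
- The 12-month infection proportion p is an assumption for this trial, set at 20%, 50%, 85.3% and 88.9%. The last two are the CFZ533 and tacrolimus figures from the kidney study in Protocol 4.7.
- The hazard is constant and equal in both arms (assumption): λ = −ln(1 − p)/336 per day.
- Stopping patterns are assumptions, because the documents give no exposure by arm.

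**Step 1: bounding case, a whole arm stopping at day 168 or at day 336.** The mean of min(T, c) is (1 − e^(−λc))/λ. For p = 20%, λ = 0.22314/336, so 1/λ = 1505.8 days. At c = 336 the mean is 0.2 × 1505.8 = 301.2 days.

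| p | stop day 168 | stop day 336 | gap (days) |
|---|---|---|---|
| 20% | 159.0 | 301.2 | 142.2 |
| 50% | 142.0 | 242.4 | 100.4 |
| 85.3% | 108.1 | 149.5 | 41.4 |
| 88.9% | 101.9 | 135.9 | 34.0 |

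**Step 2: milder case.** In one arm 20% stop early and in the other 50%, uniformly over 336 days; the rest are observed to day 336. The mean for those stopping early is (1/λ)[1 − p/(λτ)]. For p = 20% this is 1505.8 × (1 − 0.2/0.22314) = 156.2 days, so the gap is (0.5 − 0.2) × (301.2 − 156.2) = 43.5 days. A simulation of 200,000 participants per arm, without the 14-day tail, agrees:

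| p | plain mean, 20% stop | plain mean, 50% stop | gap | infected only, 20% stop | infected only, 50% stop | gap |
|---|---|---|---|---|---|---|
| 20% | 271.8 | 228.6 | 43.2 | 155.4 | 143.8 | 11.6 |
| 50% | 221.0 | 188.6 | 32.4 | 142.7 | 131.6 | 11.1 |
| 85.3% | 138.9 | 123.2 | 15.7 | 112.3 | 102.9 | 9.4 |

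Averaging only infected participants shrinks the artefact but does not remove it.

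**Step 3: the 14-day tail.** With both arms stopping at day 336, the CFZ533 mean rises to 312.3, 249.3 and 151.5 days for p = 20%, 50% and 85.3%. These are gains of 11.1, 6.9 and 2.0 days from the window definition alone. They would partly offset Step 2 if CFZ533 were the earlier-stopping arm.

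**Step 4: the adverse-event window.** It is also anchored to last dose, so the dependence remains. With CFZ533 stopping at day 168 (plus 98 days) and control at day 336 (plus 84 days), the means are 243.8 and 366.5 days at p = 20%, and 136.8 and 159.3 at p = 85.3%.

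**Step 5: censoring-aware alternatives on the Step 2 data (20% stop, then 50% stop).** The Kaplan-Meier restricted mean to day 336 is 301.0 and 301.1 days (p = 20%), 242.4 and 242.1 (50%), and 149.3 and 149.4 (85.3%). Events per 100 participant-years are 24.4 and 24.4, 75.3 and 75.7, and 208.9 and 208.5. Both recover the equality that was built in.

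**The case against.** A reader might infer that the SAP instructs the analyst to average censored times. It does not: the estimator is left open, and a programmer could implement a sound one.

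A reader might also take the on-treatment cut-off as settled. SAP 2.1.2 allows exceptions, and SAP 2.1 names infections, CMV and EBV as summarized on all eligible collected events. The text following the sentence in SAP 2.7.3 covers participants who have left CFZ533, so that block clearly uses off-treatment data. Protocol 8 and 9.1.1 keep participants who stop treatment in follow-up to Month 24. If all collected follow-up is used, stopping treatment does not by itself end observation, and the link to treatment stop weakens considerably.

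Nor do staggered entry and early termination by themselves bias the arms. Randomization was concurrent, so both affect the arms alike in expectation; a comparison is distorted only if observation time differs by arm.

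Finally, SAP 2.7 names serious infections, not this average, as the key safety parameter. Infections are also tabulated by type and severity and listed, and serious infections have their own stopping rule (SAP 3.1).

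All of this stands, and it limits the point. It does not remove it: three candidate windows with no choice among them is a gap, and a plain average depends on length of observation under each.

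**Conclusion.** The point holds as a low-severity improvement. The infection-free period is undefined, and a plain average would depend on length of observation. Under the default on-treatment rule it would depend on time on treatment, so an arm that stops earlier would look worse at equal risk.

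The illustrative size is about 16 to 43 days, for assumed 12-month infection proportions of 85.3% down to 20%. It rests on a constant, equal hazard and on 20% against 50% of an arm stopping early. The gaps of 34 to 142 days in Step 1 need a whole arm to stop at half the follow-up of the other; they are a bound, not an expectation.

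The documents do not support a claim that the reported average will favour or disfavour CFZ533. Exposure by arm is not given, and the 14-day tail can work against the stopping effect. The output is descriptive and enters no test, success criterion or stopping rule.

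**What to change.** In SAP 2.7.3:

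1. Define the start (transplantation, randomization or first dose), the qualifying infection (any, or EBV/CMV only), the observation window, and censoring. State whether death ends the infection-free period or censors it.
2. Replace the plain average with Kaplan-Meier time to first infection by arm. Add restricted mean infection-free time to one common day that follow-up supports in every arm, with a 95% CI. Alternatively, report the exposure-adjusted rate already defined in SAP 5.5.1. That rate assumes constant intensity, so the restricted mean is preferable if infection risk changes over time.
3. Use all collected follow-up where available. Censoring at treatment stop may be informative, because over-immunosuppression can lead to CFZ533 discontinuation (Protocol 6.5.2). The rate in SAP 5.5.1 as written also stops at end of treatment, so state this limitation whichever estimate is used.

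The cost is a few sentences in the SAP and slightly more programming. Kaplan-Meier methods are already planned in SAP 2.4.5, and no new data are needed.
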